2.1.2. Rationale for subject population

Myelodysplastic syndromes (MDS) are clonal disorders of the bone marrow characterized by ineffective hematopoiesis with peripheral blood-cytopenia and a propensity to transform to acute myeloid leukemia (AML). MDS may evolve into AML in up to 45% of patients [Greenberg, 1997]. Differentiation of hematopoietic stem cells is impaired in MDS. Clonal expansion of the abnormal stem cells results in the production of cells which have lost the ability to differentiate into normal blood cells [Fenaux, 2014]. In MDS patients, myeloblasts often constitute more than 5% of the cells in the bone marrow. The number of myeloblasts is one of the principal determinants of

disease severity, where the percentage of blasts of >20% constitutes a transformation to AML. MDS occurs in 3-4 individuals per 100,000 in the US population. Incidence rates increase with age. Individuals age 60 and above have a higher prevalence rate of 7-35 per 100,000 [Rollinson, 2008]. The median age at diagnosis of MDS is 73 years [Mufti, 2012].

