| 1. To evaluate clinical activity after treatment with GSK2879552, alone or in combination with azacitidine, in adult subjects with HR MDS previously treated with HMA. | 1. Clinical benefit rate (CBR) defined as % of subjects achieving CR, mCR, PR, cytogenetic response, HI or SD. Objective response rate (ORR) defined as % of subjects achieving CR, mCR, PR, cytogenetic response, or HI [as per 2006 IWG criteria]). |
| Secondary | |
| 1. To further evaluate the safety and tolerability of GSK2879552 administered alone or in combination with azacitidine. | 1. Changes in safety parameters: e.g. AEs and SAEs, changes in laboratory values, vital signs, electrocardiograms [ECGs], and physical examinations. |
| 2. To characterize the population PK of GSK2879552, alone or in combination with azacitidine in patients with HR MDS previously treated with HMA. | 2. Population PK parameters for GSK2879552 such as clearance (CL/F). |
| 3. To evaluate duration of response, duration of clinical benefit, progression-free survival, and overall survival. | 3. Duration of response (DOR) defined as the time from first documented response to disease progression. Progression free survival (PFS) defined as the time from first dosing day to disease progression or death from any cause. Overall survival (OS) defined as the time from first dosing day until death from any cause. |
| 4. To evaluate frequency and time to progression to AML (per 2006 IWG criteria) | 4. Proportion of subjects with disease progression to AML. Time to AML progression. |
| 5. To evaluate platelet and RBC transfusion dependence. | 5. Number of documented platelet and RBC transfusions per month within 3 months prior to study entry and while on study. |

| Objectives | Endpoints |
|---|--|
| Exploratory | |

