4.6. Intra-subject Monotherapy to Combination Arm Crossover

Subjects on monotherapy (Arm A) will be allowed to cross over (to Arm B) to be treated with the combination at RP2D at the time of progression. The crossover is allowed if a patient has not experienced intolerable toxicity on mono therapy, and has experienced disease progression (including AML) according to 2006 IWG criteria. In each case, approval for crossover has to be granted by GSK Medical Monitor.

The study site is required to provide the safety and disease assessment data of the subject, and the completed crossover form (Refer to Study Procedure Manual) at least 48 hrs prior to the crossover. The medical monitor will review the data and provide the approval for crossover with a signed crossover form.

The crossover to combination treatment Arm B should occur as quickly as possible and no later than within 4 weeks of disease progression. All assessments and samples required at the “crossover visit” as described in the Time and Event table (Section 7.1) must be completed at the time of crossover. The disease assessment and safety laboratory results at the time of crossover will be considered a new baseline as the subject starts combination treatment and continue on with the next visit (from the mono therapy).

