5.2. Exclusion Criteria

A subject will not be eligible for inclusion in this study if any of the following criteria apply:

DIAGNOSTIC ASSESSMENTS AND OTHER CRITERIA

1. AML according to WHO criteria (i.e. bone marrow blasts >20%)
2. Active hepatitis B or hepatitis C treatment
3. Baseline (pre-dose Day 1) Montreal Cognitive Assessment (MOCA) score of 22 or lower

CONCURRENT CONDITIONS/MEDICAL HISTORY

4. History of or concurrent malignancy of solid tumours, except for below:
Exception: Subjects who have been disease-free for 2 years, or subjects with a history of completely resected non-melanoma skin cancer or successfully treated in situ carcinoma are eligible. Consult GSK Medical Monitor if unsure whether second malignancies meet requirements specified above
5. Prior treatment with temozolomide, dacarbazine or procarbazine
6. Prior treatment with poly ADP ribose polymerase (PARP) inhibitors (e.g., olaparib, ABT-888)
7. Currently receiving other anti-cancer therapy (chemotherapy, radiation therapy, immuno-therapy, biologic therapy, hormonal therapy, surgery, and/or tumour embolization)
8. Received major surgery, radiotherapy, or immunotherapy within 4 weeks of GSK2879552 administration
9. Evidence of severe or uncontrolled systemic diseases (e.g., severe/chronic infection, unstable or uncompensated respiratory, renal, or cardiac disease). Any serious and/or unstable pre-existing medical (aside from malignancy exception above), psychiatric disorder, or other conditions that could interfere with subject's safety, obtaining informed consent or compliance to the study procedures, in the opinion of the Investigator
10. Current active liver or biliary disease (with the exception of Gilbert's syndrome or asymptomatic gallstones or otherwise stable chronic liver disease per investigator's assessment)
11. Patients with any major bleeding current or within the past 4 weeks. (e.g. recent GI hemorrhage or neurosurgery).
12. Administration of an investigational drug within 14 days or 5 half-lives, whichever is shorter, preceding the first dose of study treatment(s) in this study.
13. Cardiac abnormalities as evidenced by any of the following:
 - Clinically significant uncontrolled arrhythmias or uncontrolled hypertension.
 - History or evidence of current \geq Class II congestive heart failure as defined by New York Heart Association (NYHA)
 - History of acute coronary syndromes (including unstable angina and myocardial

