12.10. Appendix 10: IWG CRITERIA FOR RESPONSE

| Category | Response Criteria |
|------------------------------|--|
| Complete Remission | Bone marrow: $\leq 5\%$ myeloblasts with normal maturation of all cell linesa Persistent dysplasia will be noteda,b Peripheral blood (Response must be maintained for at least 4 weeks) Hgb ≥ 11 g/dL Platelets ≥ 100 Gi/L Neutrophils ≥ 1.0 Gi/Lb Blasts 0% |
| Partial Remission | All CR criteria if abnormal before treatment except: Bone marrow blasts decreased by $\geq 50\%$ over pre-treatment but still $> 5\%$ Cellularity and morphology not relevant |
| Marrow CR^b | Bone marrow: $\leq 5\%$ myeloblasts and decrease by $\geq 50\%$ over pre-treatment ^b Peripheral blood: if HI responses, they will be noted in addition to marrow CR ^b |
| HI | Erythroid (HI-E): hgb increase of > 1.5 g/dL decrease of $>$ RBC transfusions/8weeks versus pretreatment requirement in previous 8 weeks; only RBC transfusions given for a pretreatment Hgb of < 9.0 g/dL count Platelet (HI-P): increase of $> 30,000$ /mL (starting with $> 20,000$ /mL) increase from $< 20,000$ /mL to $> 20,000$ /mL by $> 100\%$ Neutrophil (HI-N): increase of $> 100\%$ and > 500 /uL |
| Stable Disease | Failure to achieve at least PR, but no evidence of progression > 8 wks |
| Disease Progression | For subjects with: 
 • Less than 5% BM blasts: $\geq 50\%$ increase in blasts to $> 5\%$ blasts • 5%-<10% BM blasts: $\geq 50\%$ increase to $> 10\%$ blasts • 10%-<20% BM blasts: $\geq 50\%$ increase to $> 20\%$ blasts • 20%-30% BM blasts: $\geq 50\%$ increase to $> 30\%$ blasts Any of the following: 
 • At least 50% decrement from maximum remission/response in granulocytes or platelets • Reduction in Hgb by ≥ 2 g/dL • Transfusion dependence |
| Non-evaluable | Subject does not meet any of the above criteria |

BM = bone marrow ; CR = complete remission; Hgb = hemoglobin;; PR = partial remission

a. Dysplastic changes should consider the normal range of dysplastic changes (modification).

b. Modification to IWG response criteria [[Cheson, 2006](#)].

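### Appendix 10 does not score some transformations to AML as progression (rises below 50% that cross 20% blasts), although Section 4.6 and the AML endpoint treat AML as progression

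*Protocol*

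**What the plan says.** Section 7.4 of the protocol names Appendix 10 as the source of the response criteria. Its Disease Progression row sets blast bands by baseline. The two upper bands are "10%-<20% BM blasts: $\geq 50\%$ increase to $> 20\%$ blasts" and "20%-30% BM blasts: $\geq 50\%$ increase to $> 30\%$ blasts". No band lies above 30%, and no line covers transformation to AML. The same row lists progression signs that do not depend on blasts: "At least 50% decrement from maximum remission/response in granulocytes or platelets", a haemoglobin fall of at least 2 g/dL, and transfusion dependence. Stable disease is "Failure to achieve at least PR, but no evidence of progression" for more than 8 weeks.

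Elsewhere the protocol treats AML as follows:
- Section 2.1.2: "the percentage of blasts of >20% constitutes a transformation to AML".
- Section 5.2, exclusion criterion 1, uses the same cut, so a subject with blasts up to and including 20% can enter.
- Section 4.6 opens crossover to a subject who "has experienced disease progression (including AML) according to 2006 IWG criteria", and makes the disease assessment at crossover the new baseline.
- Section 3, both parts, lists as an endpoint: "Proportion of subjects with disease progression to AML. Time to AML progression".

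Section 9.4.1 counts SD at any time as clinical benefit. Section 9.1.2 tests CBR per arm, 30% against 50%, and claims activity with at least 12 successes in 28.

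**The concern.** One clinical event gets two answers. A subject whose blasts go from 18% to 25% has AML by the protocol's definition and is a progressor under Section 4.6 and the AML endpoint. By the Appendix 10 blast bands the same subject has not progressed.

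This matters most because SD is a success in the tested Part 2 endpoint, so a subject who transforms could be counted as benefiting. PFS could run on after the date on which time to AML records an event. The definition of progression also feeds the trigger for the final analysis (Section 5.6, 70% of Part 2 subjects progressed or dead). The study is open-label, so leaving assessors to choose a reading once data are visible is an avoidable weakness.

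The crossover phase has a separate gap. A subject re-baselined with AML above 30% blasts has no blast criterion in Appendix 10.

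**Working it through.** **1. Where the blast rule and the AML definition part.** Let b be the baseline and y the later blast percentage.
- AML (Sections 2.1.2 and 5.2): y > 20.
- Appendix 10, 10 ≤ b < 20: progression if y ≥ 1.5b and y > 20.
- Appendix 10, b = 20: progression if y ≥ 30 and y > 30, that is y > 30.

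For b below 20, AML without blast progression needs 20 < y < 1.5b. That range is non-empty only if 1.5b > 20, so b > 20/1.5 = 13.33. At b = 20 it is 20 < y ≤ 30.

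| Baseline % | 1.5 × baseline | Whole-percent values that are AML but not blast progression |
|---|---|---|
| 13 | 19.5 | none |
| 14 | 21.0 | none (21 is exactly +50%) |
| 15 | 22.5 | 21–22 |
| 16 | 24.0 | 21–23 |
| 17 | 25.5 | 21–25 |
| 18 | 27.0 | 21–26 |
| 19 | 28.5 | 21–28 |
| 20 | 30.0 (and must exceed 30) | 21–30 |

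Example: 18% to 25% is a relative rise of 7/18 = 39%. It is AML but below the 50% condition. A rise from 18% to 27%, or from 15% to 23%, is scored as progression.

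**2. Path to a CBR success.** All of these must hold:
- blasts enter the range in step 1;
- they do so before SD of more than 8 weeks is reached (after that the subject already counts, because SD counts at any time);
- they stay in that range until SD is reached;
- no haemoglobin, count or transfusion criterion is met.

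The conflict between PFS and time to AML is not limited to early transformation. It can arise whenever the crossing occurs.

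**3. The plan's own error rates.** Exact binomial recursion through the Table 5 futility bounds (stop at ≤1/10, 2/12, 3/14, 3/16, 4/18, 5/20, 6/22, 8/24, 9/26), with a claim at ≥12/28:

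f_k(x) = (1 − p) f_{k−1}(x) + p f_{k−1}(x − 1), dropping x at or below the bound at each look.

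- p = 0.30: P(claim) = 0.0991 (Section 9.2.1 states 0.099).
- p = 0.50: P(claim) = 0.8174 (stated 81%), and 1 − 0.8174 = 0.183 (the stated early-termination probability).
- The Table 5 continuation probabilities for 10 to 26 subjects match to four decimals.

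**4. Sensitivity, on an assumed input.** The documents do not say how often such a subject occurs. Let m be the share of all subjects who are true failures but are scored SD this way, and run the same recursion at p = 0.30 + m.

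| m (assumed) | p | P(claim) |
|---|---|---|
| 0 | 0.300 | 0.099 |
| 1% | 0.310 | 0.121 |
| 2% | 0.320 | 0.147 |
| 1 in 28 | 0.336 | 0.192 |
| 2 in 28 | 0.371 | 0.320 |

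**5. Crossover.** Section 4.6 allows crossover with AML and resets the baseline. The last Appendix 10 band ends at 30%. Above that, Appendix 10 scores progression only on counts, haemoglobin or transfusion dependence. Section 9.3.1 puts these subjects in a separate Crossover Population, and no hypothesis is set for it.

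**The case against.** The strongest reply is that Section 4.6 already says AML is progression under the 2006 IWG criteria, and SD requires no evidence of progression, so AML excludes SD. Section 9.4.1 adds that PD follows standard criteria and leaves further PFS censoring rules to the analysis plan. This stands in part: the protocol does not unambiguously rule that AML is SD. But Section 4.6 governs crossover, not response scoring, and it defers to criteria whose only statement in the protocol is Appendix 10. The inconsistency remains.

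The path to a false success is also narrow, as step 2 of the working shows. Section 7.4 calls for marrow only when clinically indicated or to confirm response, so some transformations may never be seen. This stands and limits the effect on CBR.

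Three stronger readings are tempting, and the documents do not support them.
- A reader might infer that Appendix 10 never scores AML as progression from a baseline above 13.3%. It does when the rise reaches 50% (above 30% blasts when the baseline is exactly 20%).
- A reader might take the higher P(claim) values as the trial's real false-positive rate. They rest wholly on an assumed m. They also assume that the 30% reference rate counts these transformations as failures, which the protocol does not say.
- A reader might infer that the missing band above 30% favours the primary result, or that such subjects cannot progress. It lies outside the 12-of-28 test, and the other criteria still apply.

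**Conclusion.** The point holds as a contradiction within the protocol. Appendix 10 conflicts with Section 4.6 and the AML endpoint for rises below 50% that cross 20% blasts from a baseline above 13.3% and below 20% (in whole percentages, from 15%), and for any rise to 30% or less from exactly 20%. Followed literally, it can give SD and CBR, PFS and time to AML results that disagree within one subject. The arithmetic of the gap is certain; how often it occurs is not known.

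The effect on CBR is confined to early transformations without another progression sign. With 12 of 28 as the bar, even an average of one such subject per 28 would roughly double P(claim) at a true CBR of 0.30, from 0.099 to 0.19. That is an illustration, not an estimate. The missing blast row above 30% is a real but separate gap, limited to the crossover phase.

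**What to change.** Before Part 2 responses are scored, reconcile Appendix 10 with Sections 3 and 4.6, so that transformation to AML as the protocol defines it is handled the same way in endpoint scoring for SD and CBR, for PFS and for time to AML. State how blast progression is scored when the crossover baseline is above 30%. The same definition governs treatment discontinuation and crossover (Sections 4.2, 4.6 and 4.7), so those sections must be reconciled with it too. No clinical rule is proposed here; that choice belongs to the sponsor and investigators.

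The cost is a few lines in Appendix 10 and matching analysis wording, with no added procedure. The downside is that CBR and PFS may look slightly less favourable.

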| Secondary Medical Monitor | PPD [redacted] [redacted] MD, PhD PPD [redacted] MD, MPH | [redacted] | [redacted] | GlaxoSmithKline [name] PPD [redacted] |

Investigator Protocol Agreement Page

Rationale for Change

Investigator address and Phone number details were added.

Revised Text

| | | |
|-----------------------------------|--|------|
| Investigator Name: _____ | | |
| Investigator Address: | | |
| Investigator Phone Number: | | |
| Investigator Signature | | Date |

Synopsis

Rationale for Change: References were removed from the synopsis section as synopsis need to be a stand alone document. Also, study stopping criteria was modified for clarification.

Revised Text**Overall Design***2nd and 3rd paragraph*

Bayesian Logistic Regression Model (BLRM) prediction on **Dose-Limiting Toxicity** (DLT) rate may also be provided at dose escalation meetings as the supplementary analysis to 3+3 design (~~See Section 4.3.2. for more details~~). Once the RP2D of GSK2879552 for MDS is confirmed in both Arms, Part 2 enrolment will open. Each treatment cycle is 28 days and subjects experiencing disease progression on monotherapy (Arm A) will be allowed to cross over (to Arm B) to be treated with the combination at the RP2D.

The statistical design and number of subjects to be enrolled in Part 2 is based on the predictive probability of success if enrollment continues until all planned subjects are recruited [Lee, 2008]. The predictive probability design allows for evaluation of stopping rules after each subject once a minimum number of subjects are evaluable. The study will stop ~~only~~ for futility, **while also taking into account subject and study termination criteria as defined in the protocol**. Final decisions on stopping enrolment will depend on the totality of the data collected.

Type and Number of Subjects

Point 9, 10, 11 and Diagnostic assessment

| LABORATORY | |
|---|-------------|
| 9. Renal | |
| Creatinine | ≤1.5 X ULN |
| OR | |
| Calculated creatinine clearance by Chronic Kidney Disease Epidemiology Collaboration (CKD-EPI) equation (Appendix 3) or measured from 24hr urine | ≥ 50 mL/min |

| GENDER and REPRODUCTIVE POTENTIAL |
|--|
| 10. Women of childbearing potential must have a negative serum pregnancy test within 7 days of first dose of study treatment and agree to use effective contraception, as defined in Appendix 7 of this protocol , during the study and for 7 days following the last dose of study treatment. |
| 11. Men with a female partner of childbearing potential must have either had a prior vasectomy or agree to use effective contraception, as defined in Appendix 7 of this protocol , from the administration of the first dose of study treatment until 3 months after the last dose of study treatment to allow for clearance of any altered sperm. |

| DIAGNOSTIC ASSESSMENTS AND OTHER CRITERIA |
|---|
| 1. AML according to WHO criteria (i.e. bone marrow blasts >20%) [Vardiman, 2009]. |
| 2. Active hepatitis B or hepatitis C treatment |
| 3. Baseline (pre-dose Day 1) Montreal Cognitive Assessment (MOCA) score of 22 or lower |

4.11.1 Risk Assessment

Rationale for change

Text was added to clarify the term Baseline to mean pre-dose Day 1

Revised Text

| Potential Risk of Clinical Significance | Summary of Data/Rationale for Risk | Mitigation Strategy |
|---|---|---|
| GSK2879552 | | |
| Encephalopathy | Three (out of 18) subjects enrolled in 200858 study experienced encephalopathy. | 
Informed Consent Form is updated to include the risk of mental status change. Protocol eligibility and monitoring criteria are modified:
 
 - subjects who have received prior treatment with temozolomide, dacarbazine, procarbazine or PARP inhibitors are excluded - Montreal Cognitive Assessment (MOCA) at baseline (pre-dose Day 1) and weekly for the first 4 weeks and monthly thereafter. - Subjects with baseline (pre-dose Day 1) MOCA score of ≤ 22 are excluded - Protocol stopping criteria is modified: - Dosing will be held and neurology consult will be required if a decrease of 3 points or more from baseline (pre-dose Day 1) MOCA score or any score of < 22 occurs or in case of any other indication of early encephalopathy as determined by patient history or physical exam |

5. SELECTION OF STUDY POPULATION AND WITHDRAWAL CRITERIA**5.2 Exclusion Criteria****Rationale for Change**

Text was added to clarify the term Baseline to mean pre-dose Day 1

Revised Text

| DIAGNOSTIC ASSESSMENTS AND OTHER CRITERIA |
|---|
| 
 1. AML according to WHO criteria (i.e. bone marrow blasts $>20\%$) 2. Active hepatitis B or hepatitis C treatment 3. Baseline (pre-dose Day 1) Montreal Cognitive Assessment (MOCA) score of 22 or lower |

5.4.3 Mental Status Stopping Criteria

Rationale for Change

Stopping criteria were updated based on the FDA mandated language resulting from a recent Dear Investigator Letter (DIL) of encephalopathy dated 24 Apr 17 reported in LSD1 study 200858

Revised Text

Enrollment will be stopped upon the occurrence of any encephalopathy, unless clearly attributable to central nervous system disease involvement or intercurrent illness.

Study treatment will be held and neurology consult obtained if any of the 3 criteria below are met:

- A decrease of 3 points or more from baseline (**pre-dose Day 1**) Montreal Cognitive Assessment (MOCA) score (Section 7.3.7)
- Any MOCA score of <22
- Any other indication of early encephalopathy as determined by patient history or physical exam

The treatment may resume if one of the following criteria is met:

- A reversible cause other than study treatment is identified and both MOCA score and symptoms return to baseline (**pre-dose Day 1**).
- Evaluated by a neurologist and found to have no clear signs/symptoms of encephalopathy or other cognitive dysfunction. This is applicable only in the absence of decrease in MOCA score.

All treatment restarts must be approved by GSK medical monitor. The treatment should be permanently discontinued for subjects with documented symptoms with no other cause, even if they return to baseline (**pre-dose Day 1**).

6. STUDY TREATMENT

6.2.1 GSK2879552

Rationale for Change

Only two doses were to be used in the study – 0.5 mg and 2 mg. Table was updated to remove 5 mg dose.

Revised Text

| | |
|---------------------------------|--|
| Product name: | GSK2879552 Capsule |
| Formulation description: | GSK2879552 capsules contain 0.5 mg or 2 mg, 5 mg of GSK2879552 as parent. |
| Dosage form: | Capsule |
| Unit dose strength(s) | 0.5 mg, 2 mg and 5 mg |
| Route/ Regimen | Oral The initial dosing regimen will be continuous oral daily dosing. Subjects should take their doses fasted (i.e. no food intake from 2 hours before dosing until 1 hour after dosing) with approximately 200 mL of water. |
| Physical description: | 0.5 mg GSK2879552: Opaque Size 1 capsule composed of a light green body and a light green cap with no identifying markings containing a white to slightly coloured powder. 2 mg GSK2879552: Opaque Size 1 capsule composed of a pink body printed with two black lines and a pink cap printed with two black lines, containing a white to slightly coloured powder. |

